8.0 STATISTICAL CONSIDERATIONS

A sample size of 12 with a cross over design (i.e., 12 per arm) is considered adequate to estimate effect sizes for efficacy to aid in designing future trials for responses that are normally distributed [52]. Simple comparisons will be performed using chi-square for categorical variables and t-tests for continuous variables. Random attritions and failed screens will be replaced. An intention to treat analysis will not be appropriate given the crossover design. Adverse events will be presented as the proportion of each event seen. This is considered a minimal risk study with low risk for minor adverse events such as mild gastrointestinal symptoms that could be related to increased dietary fiber intake. Our primary outcome is changes in the gut microbiome profile. To determine the diversity and richness of the microbiome, we will calculate a diversity index for both the pre- and post-intervention time points for each recipient. Microbial sequence analysis and statistics will be analyzed using the Quantitative Insights into Microbial Ecology (QIIME) 1.8.0 software as previously described [53].

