1.2 Overview

Given these promising findings in animal models of T1D as well as adult non-diabetic studies, we hypothesize that HAMS-AB will alter the gut microbiome profile in humans with T1D and increase SCFA production and that these changes will be associated with improved β -cell function, overall glycemia, and β -cell health (as measured by markers of β -cell stress and death). We plan to perform a pilot, randomized, controlled cross-over trial of HAMS-AB in 12 individuals with recently diagnosed T1D to determine HAMS-AB effects on the gut microbiome profile, SCFA production, glycemia, markers of β -cell function, stress, and death.

This pilot study is a single center trial. Twelve newly diagnosed T1D youths with a BMI<85% and within 4-36 months of diagnosis who have measurable endogenous insulin production, assessed using serum C-peptide, and are, therefore, in the honeymoon period, will be recruited. We have chosen this cohort since the microbiome profile differs by age [29] and BMI [30], and the progression of T1D differs between children and adults [31]. Additionally, there is ample published experience studying healthy adolescents and their microbiome changes with corn fiber supplementation [32, 33], and therefore, we have chosen to pilot this intervention in a similar age group with known published data. In addition, to assess changes more accurately in β -cell function, we will include those in the honeymoon period as there is sufficient measurable C-peptide secretion during this time. The honeymoon period is the time shortly after T1D diagnosis when the β -cells undergo partial and temporary recovery and produce enough insulin to reduce insulin needs and aid with glycemic control [34, 35].

The **objectives** of this study are to assess the HAMS-AB effects on the gut microbiome profile, SCFA production, glycemia and β -cell health and function in humans with T1D. We **hypothesize** that HAMS-AB will (i) improve the gut microbiome profile in humans with T1D, (ii) increase SCFA production, and (iii) improve β -cell function, β -cell health and overall glycemia. We propose the following Specific Aims:

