AIM 1: Determine the effect of HAMS-AB on the gut microbiome profile and SCFA production in children with recently diagnosed T1D. We *hypothesize* that HAMS-AB consumption will shift the gut microbiome to microbial populations that are capable of HAMS-AB fermentation and increase SCFA production. Twelve youths (11-17 years old) will consume HAMS-AB or follow the standard of care recommended diabetic diet daily for [49,50] 4 weeks and then cross over after a 4-week washout period. DNA will be extracted from fecal samples obtained followed by 16S RNA sequencing for gut microbial community analysis at baseline and at each visit during the study period [32, 33]. SCFAs will be analyzed using standard methods [36, 37].

AIM 2: Determine the effect of HAMS-AB on glycemia and β -cell function and health. We *hypothesize* that the prebiotic HAMS-AB will improve overall glycemia including reducing glycemic variability in recently diagnosed persons with T1D. We will compare glycemic/ β -cell measures pre/post intervention with HAMS-AB and between the intervention and control groups. We will measure glycemia using HbA1c, average glucose and glucose variability using continuous glucose monitoring (CGM) [38-40]. We expect to see an improvement in glycemia in response to HAMS-AB intake. We will assess β -cell function using mixed meal tolerance (MMTT)-derived C-peptide measures. We *expect* that measures of β -cell stress/death will show improvement following the use of HAMS-AB. We will determine β -cell stress using proinsulin/C-peptide (PI:C) ratios [41]. We will assess β -cell death by differential methylation of proinsulin (INS) DNA [42].

Upon successful completion of this pilot study, we expect to assess the effect of prebiotic administration on the gut microbiome profile, SCFA production, glycemia and β -cell function in humans with T1D. The knowledge generated by the proposed research will provide critical experimental information needed to substantiate a fully powered study.

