33 ENROLLMENT

Up to 24 subjects will be screened to find 12 adequate subjects eligible for enrollment.

The plan is to recruit 24 patients with the goal of having 50% eligible and enrolled. Once 12 participants have completed the 12 week visit, we will stop recruitment. At Indiana University, as per our current recruitment strategies for other new-onset studies, patients with newly diagnosed T1D will be approached whenever possible when inpatient at diagnosis and then re-contacted after discharged home. Visits will be conducted at the Indiana Clinical Research Center (ICRC) and coordinated with diabetes clinic follow-up visits when possible.

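### Section 8.0 plans simple t-tests and chi-square tests for a 12-participant two-period crossover, and states neither a within-participant comparison nor a period term

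*Combined protocol and SAP*

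**What the plan says.** Section 8.0 is the whole statistical plan. For treatment comparisons it names one approach: "Simple comparisons will be performed using chi-square for categorical variables and t-tests for continuous variables". The size is justified by "A sample size of 12 with a cross over design (i.e., 12 per arm", as adequate for estimating effect sizes that will help design later trials. For the microbiome, "we will calculate a diversity index for both the pre- and post-intervention time points for each recipient", and "Microbial sequence analysis and statistics will be analyzed using the Quantitative Insights into Microbial Ecology (QIIME) 1.8.0 software", following a cited publication.

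Aim 2 (Section 1.2) says glycemic and β-cell measures will be compared "pre/post intervention with HAMS-AB and between the intervention and control groups", and lists them: "We will measure glycemia using HbA1c, average glucose and glucose variability using continuous glucose monitoring (CGM"), alongside MMTT C-peptide and stress and death markers.

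Section 6.2 assigns six participants to each order. Section 3.3 says: "Once 12 participants have completed the 12 week visit, we will stop recruitment". Sections 3.2, 6.2 and 8.0 allow replacement of participants, and none says whether a replacement takes the sequence of the person replaced.

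The only repeated-measures model with a sequence term in the document is in the legend to Figure 2, and it describes a cited study.

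**The concern.** In a two-period crossover each participant serves as his or her own control. That advantage is obtained only if the analysis is within participant. A period term is the usual companion, because anything that changes with time otherwise enters the error, or the estimate if the sequences are unequal.

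The text points both ways on pairing. Computing the index per recipient suggests paired values, although it describes a summary and not a test. Counting 12 per arm and comparing groups reads like independent samples.

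Time trends are plausible here for C-peptide and glycemic outcomes, because the protocol describes the honeymoon as a phase when β-cells "undergo partial and temporary recovery and produce enough insulin to reduce insulin needs and aid with glycemic control". The end-of-period visits, 3 and 5, are two 28-day intervals apart.

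The pilot exists to supply an effect estimate, its precision and a usable SD. Those are the quantities that depend on which test is run.

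**Working it through.** **The plan's own figure.** 6 + 6 = 12 participants, each under both conditions, gives 12 observations per condition, which matches the stated 12 per arm. The 12 cannot be reproduced from a power formula: no alpha, power, effect or SD is given, and the reference list shows a per-group rule of thumb for pilots.

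**Inputs.** From the documents: n = 12, split 6:6 (Section 6.2), end-of-period values at Visits 3 and 5 (Section 6.3). Assumed: between-person SD = 1; correlation ρ between a participant's Visit 3 and Visit 5 values of 0.3, 0.5 or 0.7; drift g between those visits of 0, 0.2 or 0.5 SD. The variance of a within-participant difference is v = 2(1 − ρ), that is 1.4, 1.0 and 0.6.

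**Step 1: unpaired against period-adjusted, 95% half-width.**
- Unpaired: t(22) × √(2/12) = 2.074 × 0.408 = 0.85 at any ρ.
- Period-adjusted: t(10) × √(v(1/n1 + 1/n2)/4), with t(10) = 2.228. At 6:6 this is 0.761, 0.643 and 0.498.

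**Step 2: paired, no period term, 6:6.** Drift cancels from the mean difference but raises its variance to v + g² × 12/11. The half-width is t(11) × √(variance/12), with t(11) = 2.201. At ρ = 0.7:

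| Drift g | Variance | Half-width, no period term | Half-width, period-adjusted |
|---|---|---|---|
| 0 | 0.600 | 0.49 | 0.50 |
| 0.2 | 0.644 | 0.51 | 0.50 |
| 0.5 | 0.873 | 0.59 | 0.50 |

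The variance is overstated by the factor 1 + g² × (12/11)/v. That is 3%, 4% and 7% at g = 0.2, and 19%, 27% and 45% at g = 0.5, for ρ = 0.3, 0.5 and 0.7.

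**Step 3: unequal sequences.** The unadjusted difference is biased by g × (n1 − n2)/12. At 7:5 this is 0.03 SD (g = 0.2) or 0.08 SD (g = 0.5); at 8:4 it is 0.07 or 0.17 SD. The period-adjusted estimate is unbiased, with half-width 0.51 at 7:5 and 0.53 at 8:4 (ρ = 0.7). If dropouts fall at random and replacements are allocated 1:1 at random (both assumed), the final split is not 6:6 with probability 50%, 61% and 70% after 1, 2 and 4 replacements. It is 8:4 or worse with probability 0%, 11% and 25%.

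**Step 4: error rates.** In simulation (40,000 replicates; ρ 0.3 to 0.7, drift up to 0.5 SD, 6:6 to 8:4) the paired interval without a period term covers 94% to 98%. With no drift, the unpaired test rejects a true null about 2.2%, 0.9% and 0.2% of the time at ρ = 0.3, 0.5 and 0.7. It is conservative.

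**Step 5: HbA1c, by schedule.** Sections 6.3 and 6.4 list HbA1c at Visits 2 and 5, and at early termination, but not at Visits 3 or 4. Visit 2 precedes both conditions and Visit 5 follows both. There is no value at the end of period 1, so no participant has one HbA1c per condition.

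**Step 6: use of pre-period values, ρ = 0.7, 6:6.** If all four visits are equally correlated, half-widths are 0.50 (end values), 0.54 (pre-period values as covariate) and 0.70 (raw change scores). If correlation decays with time, with Visits 3 and 5 still at 0.7, they are 0.50, 0.49 and 0.54. At 0.5 with decay they are 0.64, 0.65 and 0.73. The documents support neither structure over the other.

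**The case against.** The strongest reply is that this is a small pilot whose text already leans towards pairing, and that a competent analyst would pair. Section 3.4 also says that glycemic and MMTT outcomes are not expected to be adequately powered. This lowers the stakes but does not settle the method: neither pairing nor period adjustment is written down, and the groups wording in Aim 2 points the other way.

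The period-term part is modest. At 6:6 there is no bias, and at 0.2 SD drift the loss is 0.01 SD. A 0.5 SD drift has no support in the documents, and the honeymoon rationale does not extend to the microbiome or SCFA. This stands. So does the point that imbalance is possible but not shown, since the number of replacements and their allocation are not given.

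The next trial may be parallel-group. It would then need the between-person SD, which an unpaired analysis approximates. This stands too, and both SDs should be reported.

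The declared outcomes are changes (Sections 3.4 and 8.0), so moving to end-of-period values alone would alter the estimand. Step 6 shows that precision does not justify setting baselines aside. The fix keeps the change.

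Four stronger readings are tempting and not supported. The plan does not say the tests are unpaired. Inflated false positives do not follow, given Step 4. The primary diversity analysis cannot be called wrong, because the cited QIIME method, not available here, may specify its own test. And HbA1c is not useless: it can still be described, or compared between sequences at Visit 5, but that is not the within-participant comparison of conditions.

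**Conclusion.** The point holds as an omission that should be corrected before analysis. Section 8.0 leaves the treatment comparison open between readings with materially different precision: a half-width of 0.85 SD unpaired, against 0.76 to 0.50 period-adjusted for ρ from 0.3 to 0.7. Leaving out only the period term costs little at 6:6 unless drift is near 0.5 SD. With unequal sequences it adds a bias of at most 0.17 SD in the cases examined, below the interval half-width. All of these sizes rest on assumed correlations and drifts.

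The HbA1c point needs no assumption: the visit schedule cannot supply the within-participant comparison in Aim 2. It is a schedule limit that no choice of test repairs.

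The finding bears mainly on continuous outcomes other than the diversity index. The same sentence's chi-square test has the same pairing problem for binary outcomes observed under both conditions.

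**What to change.** Replace the sentence on simple comparisons in Section 8.0 with wording such as:

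> Continuous outcomes will be compared between conditions within participant by a period-adjusted crossover analysis (treatment and period as fixed effects, sequence included, participant random). We will report the treatment difference, its 95% CI, the within- and between-participant SD, and the number completing each sequence. Binary outcomes observed under both conditions will be compared by a paired method such as McNemar's test.

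Then add:
- Where pre-period and end-of-period values both exist (Visits 2/3 and 4/5), keep the pre/post change as the declared outcome, with pre-period values as covariates, and report the end-of-period contrast beside it. Note that Visit 4 values may carry over, since Section 3.1 looks for a durable effect after washout.
- For MMTT C-peptide (Visits 3 and 5 only) use end-of-period values; for CGM use a summary of each period.
- Apply this analysis to the diversity index unless the cited QIIME method specifies its own within-participant test.
- State in Section 8.0 and Aim 2 that HbA1c is summarised descriptively.
- Clarify the 12 per arm as 12 participants each observed under both conditions, six per sequence.

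No new visits or data are needed. With no drift, the period term moves the half-width from 0.49 to 0.50 SD (ρ = 0.7, 6:6). Under equal correlation the covariate adds about 0.04 SD at ρ = 0.7. The same ratio, 0.54/0.50 = 1.08, applied to 0.76 at ρ = 0.3 gives 0.82, or 0.06 more. Under decaying correlation it adds nothing at ρ = 0.7 and about 0.01 at 0.5. Aim 2 gives up an HbA1c comparison that the schedule does not allow.

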35 STUDY RISKS

Risks include those risks related to taking HAMS-AB, having blood draws, mixed meal tolerance tests (MMTT), risk of CGM use, and the possible loss of confidentiality.

Risks of Taking HAMS-AB:

Given that most youths in the United States are consuming less than the recommended dietary intake of fiber, we anticipate the following risks:

- Likely (reported in >20% of patients): initial abdominal discomfort, increase in frequency of bowel movements, although not to the extent of causing diarrhea. These mild intestinal symptoms will likely last for only the first few days and are self-limited without intervention.

Risk of Blood Draws:

The insertion of a needle can cause some local pain and can result in bruising. Blood draws can in rare instances cause lightheadedness or fainting. There is also a risk of infection. To mitigate these risks, blood draws will be performed by trained technicians or nurses using standard aseptic techniques.

Risk of MMTT:

There are no known risks to an MMTT, but the taste of the Boost may not be well tolerated. Some persons may experience nausea after drinking Boost. Subjects with milk or soy allergies will be excluded to avoid any allergic

reactions to Boost. If the blood glucose is high at the end of the test, subjects will be instructed to give an insulin correction dose.

Risks related to CGM use:

The CGM/sensor may produce pain when it is inserted into the skin. There is a low risk for developing a local skin infection at the site of the sensor needle placement. Itchiness, redness, bleeding, and bruising at the insertion site may occur as well as local tape allergies.

Loss of Confidentiality:

There is the unlikely chance that health information is viewed by someone outside of the research team who is not authorized to see health information. All files will be kept in locked cabinets within a locked room. Any electronic data will be protected by password systems.

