36 STUDY BENEFITS

While receiving HAMS-AB, there are potential benefits in reduction of β -cell stress for these patients. Since the gut dysbiosis may be important in the pathogenesis of T1D, accentuate β -cell stress, and have a role in the complications of the disease, these studies are of scientific importance. The benefits to be derived by mankind are expected to be substantial and may lead to advances in the prediction, prevention, and treatment of type 1 diabetes. If this study indicates that treatment can safely preserve beta cell health, then it will be a major advance in the care of diabetes.

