6.1 STUDY DESIGN

6.2 RANDOM ASSIGNMENT

Subjects will be randomly assigned (6 in each arm) to either HAMS-AB plus a recommended diabetic diet or control diabetic diet alone [49, 50] for the first 4 week of treatment period. After a suitable washout period during which participants do not need to follow the recommended diet or use the supplement, subjects will continue for 4 weeks after a cross-over. All participants will be expected to follow the guidelines for a healthy diabetic diet during the study period, except for during the 4-week washout period.

A computer-based randomization plan will be prepared by the principal investigator. The document will be kept by the study team for use. As a subject is screened and qualifies, he/she will be assigned in order of screening date on the computer-generated document. One master list will be maintained in a confidential central shared folder for use. Subjects will be replaced on an ongoing list if they drop out.

Participants will be instructed to consume HAMS-AB with food, such as apple sauce or oatmeal, in two divided doses at breakfast and dinner at a total daily dose to be calculated as has been previously described for children: 10g plus 1g per year of age daily [44]. The prebiotic will be dispensed by the Investigational Drug Services (IDS) at Indiana University.

HAMS-AB will be in the form of acetylated and butyrylated **HYLON® VII** corn starch.

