6.3 SCHEDULE OF EVENTS

Study Phase	Screening	Baseline- Intervention	Washout	Crossover- Intervention	Follow-Up	Early Termination Visit
Visit Number	1	2	3	4	5	
Visit Window		≤30 days after Visit 1	+/- 3 days 28 days after Visit 2	+/- 3 days 28 days after Visit 3	+/- 3 days 28 days after Visit 4	
Informed consent/Accent	X					
Inclusion/Exclusion criteria	X					
Historical Data/Demographics*	X					
Pancreatic Autoantibodies †	X					
Random C-peptide concentration††	X					
Randomization		X				
Pregnancy test**	X	X	X	X	X	X
Current Medical data***		X	X	X	X	X
Pubertal Tanner staging with physical exam	X					
Ht/Wt measurement and vitals	X	X	X	X	X	X
Supervised CGM insertion (and training, if applicable on use) †††		X		X		
C-peptide by 2-hr MMTT††††			X		X	X
HbA1c		X			X	X
Blood samples for biomarkers (PI:C and INS DNA)		X	X	X	X	X
Provision of HAMS-AB		X		X		
CGM download			X		X	X
Stool samples****		X	X	X	X	X
Whole blood for additional T1D testing		X	X	X	X	X
Serum and plasma for storage^		X	X	X	X	X
Adverse event assessment*****		X	X	X	X	X
Dietary Assessments*****		X	X	X	X	X
Verbal Diet recall	X					
Sampling of prebiotic	X					

Data Collection:

***Historical data:** Date of birth, sex, Race/Ethnicity, date of diagnosis of T1D.

**To be done in girls of reproductive potential.

*****Current Medical Data (All visits except screening):** Medication use including types of insulin, means of insulin administration, and total daily insulin dose (u/kg body weight, averaged over the 3 days prior to each study visit), use of other medications.

******Stool samples** will be collected at home using a kit (Zymo feces catcher and RNA/DNA shield fecal collection tubes) within 3 days of presentation to each visit.

*****Participants will be assessed for **safety** with questions regarding general well-being as well as specific questions to evaluate for adverse events. Participants will also be questioned about stool form and frequency, gastrointestinal symptoms, fevers, or infection.

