7.3 ADVERSE EVENTS

An adverse event is defined as any unintended or abnormal clinical observation that is not of benefit to the patient. Either the condition was not present prior to exposure to study supplement, or it has worsened in intensity or frequency following exposure to the study supplement. Adverse events will be graded according to the National Cancer Institute (NCI) Common Terminology Criteria v5.0.

https://ctep.cancer.gov/protocolDevelopment/electronic_applications/docs/CTCAE_v5_Quick_Reference_5x7.pdf

Any suspected or confirmed toxicity should be reported immediately (within 24 hours) to the principal investigator.

Hypoglycemic and hyperglycemic events that are seen as part of daily diabetes management will not be considered adverse events unless they result in hospitalization

Principal investigators (PI) will report to the IRB as soon as possible, but in all cases within 5 working days from notification any event that appears on the List of Events that Require Prompt Reporting to the IUPUI IRB.

List of Events that Require Prompt Reporting to the IUPUI IRB: Any of the following:

- Event (including adverse events, injuries, side effects during the research study), which in the opinion of the PI
 - caused harm to one or more subjects or others, or placed one or more subjects or others at increased risk of harm; AND
 - was unexpected; AND
 - was related to the research procedures

Note: After the study is closed with the IRB, these events will only be reported if they are profound, or they demonstrate long-term risks that would necessitate notifying subjects.

- Protocol deviation/violation (as defined under this policy)
- Change to the protocol taken without prior IRB review to eliminate apparent immediate hazard to a research subject (e.g., purposeful and for subject safety)
- Complaint of a subject that indicates unexpected risks, or complaint that cannot be resolved by the research team
- Interim findings and safety monitoring reports that indicate an unexpected change to the risks or potential benefits of the research, in terms of severity or frequency
- Publication in the literature that indicates an unexpected change to the risks or potential benefits of the research
- Change in FDA labeling or withdrawal from marketing of the supplement used in this research study
- Noncompliance (as defined in this policy)

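### Section 8.0 plans one proportion per adverse event, with no split by condition and no denominator, so the planned presentation would not show the rate on HAMS-AB or its difference from diet alone

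*Combined protocol and SAP*

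**What the plan says.** All references are to the combined protocol and SAP.

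- **Summary rule.** Section 8.0 has one sentence on how adverse events will be summarised: "Adverse events will be presented as the proportion of each event seen". It does not mention condition, period, sequence, grade or denominator.
- **Design.** Section 8.0 describes "A sample size of 12 with a cross over design (i.e., 12 per arm"). Section 6.2 states: "Subjects will be randomly assigned (6 in each arm) to either HAMS-AB plus a recommended diabetic diet or control diabetic diet alone". Aim 1 in section 1.2 gives each condition "daily for [49,50] 4 weeks and then cross over after a 4-week washout period".
- **Collection.** The schedule in section 6.3 has adverse events assessed at visits 2, 3, 4 and 5 and at early termination, with specific questions on stool and gastrointestinal symptoms. Section 7.3 grades events by CTCAE v5.0.
- **Definition.** Section 7.3 anchors an adverse event to the supplement: "Either the condition was not present prior to exposure to study supplement, or it has worsened in intensity or frequency following exposure to the study".
- **Expected events.** Under the risks of HAMS-AB, section 3.5 lists "Likely (reported in >20% of patients): initial abdominal discomfort, increase in frequency of bowel movements". No rate is given for diet alone or washout.
- **Who is counted.** Section 3.2 replaces participants who miss 20% of doses (11 of 56), sections 6.2 and 8.0 replace dropouts, and section 8.0 sets intention to treat aside. No safety set is defined.

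**The concern.** Each participant is meant to spend 4 weeks on HAMS-AB, 4 in washout and 4 on diet alone. One figure per event does not say in which of these the event arose. Background events are to be expected: section 3.5 mentions nausea after the Boost drink and skin reactions to the CGM sensor, and the schedule places meal tests and sensor use in both intervention periods. Without a split, such events sit in the same figure as any effect of the supplement.

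The missing denominator matters because of the replacement rules. A participant who stops HAMS-AB or misses doses because of abdominal symptoms is replaced, and a percentage over completers would leave that person out.

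Section 1.2 says the pilot should supply information for a fully powered study. The tolerability figures such a study would need are the rate on HAMS-AB and its difference from diet alone.

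**Working it through.** **Participants per condition.** Section 6.2 gives 6 per sequence, and everyone receives both conditions: 6 + 6 = 12 per condition. This agrees with the figure in section 8.0. That figure rests on a cited rule of thumb; the plan gives no adverse event rate, alpha or power, so there is no further calculation to reproduce.

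**What one pooled count says about the conditions.** Suppose the report gives only the number of participants ever affected, E of 12. Let a be those affected on HAMS-AB but not control, b on control but not HAMS-AB, c on both, and w in washout only, so a + b + c + w = E.

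- HAMS-AB rate = (a + c)/12
- Control rate = (b + c)/12
- Difference = (a - b)/12, which runs from -E/12 to +E/12

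Every pair of HAMS-AB and control counts from 0 to E is possible, so there are (E + 1)² pairs. The values of E are illustrations.

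| Ever affected | Difference, percentage points | Possible pairs |
|---|---|---|
| 3 of 12 | -25 to +25 | 16 |
| 4 of 12 | -33 to +33 | 25 |
| 6 of 12 | -50 to +50 | 49 |

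For E = 4, the report would look the same for 4/12 against 0/12, 0/12 against 4/12, 4/12 on both, or every event in washout.

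**Denominator.** If each of four affected participants has the event in one period, the result is 4/12 = 33% of participants, 4/24 = 17% of treatment periods, or 4/36 = 11% of periods including washout. Replacement adds to this. If k participants stop with the event and are replaced, the percentage is E/12 over completers and (E + k)/(12 + k) over everyone who entered. With E = 4 and an assumed k = 1, that is 4/12 = 33% against 5/13 = 38%.

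**Are such events likely?** At a rate of exactly 20%, the lower edge of the section 3.5 category, P(at least 1 of 12) = 1 - 0.8^12 = 0.93 and P(at least 3 of 12) = 0.44.

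**What a table by condition would show.** Take 4/12 on HAMS-AB and 0/12 on control, again as an assumption. The exact two-sided 95% intervals are 10% to 65% and 0% to 26% (upper limit for 0/12: 1 - 0.025^(1/12) = 0.265). The exact paired p-value for 4 against 0 discordant participants is 2 × 0.5^4 = 0.125. The table shows both the rate and the difference, but only descriptively.

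**Effect of the definition.** Read literally, section 7.3 does not clearly cover events on diet alone in the 6 control-first participants, who have not yet had the supplement. Control-period events might then be recorded from only 6 of 12 participants, while HAMS-AB events come from all 12. A table by condition built on that definition would favour control.

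**The case against.** The strongest reply is that the plan is brief on this point rather than wrong. Section 8.0 does not say that events will be pooled, and the same paragraph foresees comparisons of categorical variables by chi-square, so a table by condition is not excluded. That stands as far as it goes: pooling is a reading of the sentence. But the chi-square sentence does not name adverse events, assumes independent groups and supplies no denominator.

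A reader might infer that the information is lost. It is not. Visits 3, 4 and 5 close the first period, the washout and the second period, so the reporting visit already places most events. The limitation lies in the planned presentation.

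A reader might also infer that the trial sets out to show safety, since section 3.6 says "If this study indicates that treatment can safely preserve beta cell health". That is a conditional remark about benefits. Safety is absent from the objectives (2.1, 2.2) and the endpoints (3.4), and section 8.0 calls the study minimal risk.

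Finally, the gain from a table is limited with 12 participants. The control is diet alone with no placebo, so differences in subjective gastrointestinal complaints stay open to expectation effects. This is correct, and it is why the comparison should be labelled descriptive.

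**Conclusion.** The point holds as a shortcoming of the planned presentation. Taken as written, section 8.0 would show neither the adverse event rate on HAMS-AB nor its difference from diet alone, and it leaves open whether participants who stop or are replaced are counted. With 4 of 12 ever affected, differences from -33 to +33 percentage points are all compatible with the report. That range assumes a participant-level count over 12, which the plan does not state; a different denominator would add to the ambiguity.

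The documents do not support a figure for how far a pooled proportion would overstate the HAMS-AB rate. They give no background rate, nothing on dependence between periods, and a definition that may not count events before the first exposure.

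The change is worth making because it is cheap and the data will exist. It does not affect the primary outcome or the sample size.

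**What to change.** In section 8.0, replace the sentence on adverse events with a rule along these lines:

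- For each event type and CTCAE grade, report the number and percentage of participants with at least one event whose onset falls in the HAMS-AB period, the control period and the washout.
- Use as denominator everyone who entered that period, including those later replaced, with exact 95% confidence intervals.
- For gastrointestinal events, give the paired HAMS-AB minus control difference, labelled descriptive.
- Assign events by onset date where known, otherwise by the visit at which they were collected: visit 3 for the first period, visit 4 for washout, visit 5 for the second. Events reported at early termination belong to the period the participant was in.

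Keep washout as one row. Splitting it by preceding condition leaves about 6 per cell, where 0 of 6 still allows up to 46% (1 - 0.025^(1/6) = 0.459).

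In section 7.3, apply the adverse event definition equally to control periods, so that events before first exposure in control-first participants are recorded in the same way.

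The cost is one table, a short addition to section 8.0 and a wording change in section 7.3, with no extra visits or participants. The intervals will be wide (0 of 12 allows up to 26%), and the table cannot separate expectation effects from supplement effects.
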